### 3.2 END OF STUDY DEFINITION

At 12 weeks postop patients will have ASES, SANE, and Penn shoulder scores calculated. This will conclude their participation in the study.

## 4 STUDY POPULATION

### 4.1 INCLUSION CRITERIA

- Between ages 18 and 100 years old
- Scheduled for shoulder surgery
- Capable of providing informed consent (cognitively intact if consenting to surgery)

### 4.2 EXCLUSION CRITERIA

- Any surgical indication other than shoulder surgery
- Any comorbidities making surgery unsafe for the patient
- Any other condition or events considered exclusionary by the PIs and/or physician Co-Is.

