## 1 PROTOCOL SUMMARY

### 1.1 SYNOPSIS

Title:	Nerve block with liposomal bupivacaine yields fewer complications and similar pain relief when compared to an interscalene catheter for arthroscopic shoulder surgery: a randomized controlled trial
Study Description:	This is a blinded, randomized controlled trial to compare the control arm (continuous ropivacaine ISC) to the experimental arm (single-injection, brachial plexus nerve block using liposomal bupivacaine) in patients undergoing outpatient arthroscopic shoulder surgery at a single, tertiary academic institution.
Objectives:	

• Compare complication rates

• Compare pain level, dose frequency of prescribed opioid analgesics, consumption of prescribed nonopioid analgesics, quantity and quality of sleep, and overall satisfaction with pain control

• Compare patient-reported outcome measures

Endpoints:	

• Patient reported complications on post-op day 0, 1, 2, 3, and 4

• Visual Analog Scale, prescribed opioid analgesic dose frequency, consumption of prescribed nonopioid analgesics, hours of uninterrupted sleep, subjective quality of sleep (0-10 scale), and pain control overall satisfaction (five-point Likert scale) on post-op day 0, 1, 2, 3, and 4

• Visual Analog Scale, Single Assessment Numeric Evaluation, American Shoulder and Elbow Surgeons Standardized Shoulder Assessment Form, and Penn Shoulder Score at 12 weeks post-op

Study Population:	Patients greater than 19 years of age undergoing outpatient arthroscopic shoulder surgery
Phase:	Not Applicable

Description of Study Intervention:	Patients in the ISC arm will have a 19 gauge Arrow Continuous Nerve Catheter (Teleflex, Wayne, PA, USA) placed with a bolus of 15-20 mL of 0.5% ropivacaine given through the needle prior to threading the catheter. An elastomeric, basal-only, On-Q infusion pump (Avanos Medical, Alpharetta, GA, USA) with 0.2% ropivacaine will be started in the post-anesthesia care unit at 8 mL/hour, and the catheter will be removed by the patient after two days. For patients in the LB arm, 10 mL (133 mg) of liposomal bupivacaine (Pacira BioSciences, Parsippany, NJ, USA) mixed with 7 mL (35 mg) bolus of 0.5% bupivacaine will be injected.
Study Duration:	January 1, 2020 to December 1, 2021
Subject Duration:	3 months

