## 7 STUDY ASSESSMENTS AND PROCEDURES

## 7.1 STUDY ASSESSMENTS

- twice-daily phone calls for the first 4 days post-surgery

At each phone call, the following surveys will be performed:

- Medication Intake Survey
  - Since the last phone call:
    - Which medications have been consumed?
    - How many pills?
- Pain Survey
  - On a scale of 1-10, with 10 being the worst, what is your pain right now?
- Sleep Quality Survey
  - On a scale of 0-5, with 5 being the best, how was your sleep last night?
  - How many hours were you able to sleep before being interrupted by pain?

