## 8 STATISTICAL CONSIDERATIONS

### 8.1 STATISTICAL HYPOTHESES

- Primary Efficacy Endpoint(s): Postoperative Pain Scores
- Secondary Efficacy Endpoint(s): Postoperative Oral Morphine Equivalents, Analgesia Satisfaction, Analgesia Complications, Sleep Quality, and Hours of Painless Sleep

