### 8.2 SAMPLE SIZE DETERMINATION

A power analysis was conducted at 0.8 with an alpha of 0.05, using liposomal bupivacaine and ISC complication rates calculated from prior literature.

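### Preoperative opioid use is neither recorded nor used in the analysis, and the plan does not say which opioids count, so the secondary opioid comparison may lose precision and a chance imbalance in prior users could not be seen

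*Combined protocol and SAP*

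**What the plan says.** **Eligibility.** Section 4.1 asks for an age range, capacity to consent and "Scheduled for shoulder surgery". Section 4.2 excludes "Any surgical indication other than shoulder surgery" and "Any comorbidities making surgery unsafe for the patient", and leaves anything else to the investigators' judgment. Opioids are not named in either list.

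**Baseline data.** Section 3.1 collects demographics and four pain or shoulder scores (VAS, SANE, ASES, Penn). Section 8.3 compares age, BMI, operative time, gender, tobacco, ASA class, CCI, procedures and similar items. Neither mentions opioid or other analgesic use before surgery.

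**Opioid endpoints.** The synopsis (1.1) sets as an objective the "dose frequency of prescribed opioid analgesics". Section 8.1 lists "Postoperative Oral Morphine Equivalents" first among the secondary endpoints, with no limit to any one source of opioid. Section 3.1 names oxycodone, taken as needed, as the discharge opioid.

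**Capture and analysis.** At each call, the survey in 7.1 asks "Which medications have been consumed" since the last call, and how many pills. It does not separate a usual home opioid from the discharge supply. Section 8.3 compares medication consumption by Mann-Whitney U, with no stratum, covariate or baseline subtraction.

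**The concern.** A patient who already takes opioids before surgery can be expected to report different postoperative opioid use from one who does not, whichever block is given. That makes prior use a likely strong predictor of the opioid endpoints. It is known before randomization and can be read from a medication list, yet the plan neither records it nor uses it.

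The missing definition adds to this. If all opioids count, as 8.1 allows, usual intake may be scored as postoperative need. If *prescribed* in 1.1 means discharge oxycodone only, a patient drawing on home supply looks opioid-sparing. The same patient could score high on one endpoint and low on the other.

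Reduced opioid consumption is one of the potential benefits claimed in 2.3.2. A noisier comparison makes a non-significant opioid result more likely, and a non-significant result is easily read as similarity. A chance excess of prior users in one arm could also create or hide a difference, and the planned baseline table would not show it.

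**Working it through.** **Nothing to reproduce.** Section 8.2 says only: "A power analysis was conducted at 0.8 with an alpha of 0.05, using liposomal bupivacaine and ISC complication rates calculated from prior literature". It gives no rates, effect size, SD or N, and no power is claimed for any opioid endpoint. All figures below are illustrations on assumed values.

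**Assumptions, none from the documents.**
- 60 patients per arm, two-sided alpha 0.05.
- Log consumption normal with mean 3 and SD 0.9.
- Block effect -0.48 on the log scale: exp(-0.48) = 0.62, a 38% reduction.
- Prior users are 10% to 30% of patients.
- 4,000 simulated trials per setting. The simulation error is about 1.96 × √(0.7 × 0.3 / 4000) = 0.014, or 1.4 percentage points.

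**Model A: users consume a multiple, and the block reduces all of it.** Users are shifted by 0.5, 1.0 or 1.5 on the log scale: exp(0.5) = 1.6, exp(1.0) = 2.7, exp(1.5) = 4.5 times.

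**Model B: home intake is an added amount that the block does not change.** Home intake is log-normal with a median three times that of non-users.

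| Setting | Plain Mann-Whitney, 10% to 30% users | Stratified (van Elteren) |
|---|---|---|
| No prior users | about 80% | about 80% |
| A, 1.6 times | about 80% to 77% | about 80% |
| A, 2.7 times | about 77% to 71% | about 80% |
| A, 4.5 times | about 72% to 60% | about 80% |
| B, added amount | about 68% to 42% | about 75% to 61% |

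Under model A with users at 4.5 times, type I error was 4-5% for both tests, so the plain test is valid and merely less sensitive.

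**A second model as a check.** Take 63 per arm and an effect of 0.5 SD, with users shifted by m SDs of the non-user distribution. Simulated Mann-Whitney power was 79% with no users, 77% (5% users, m = 1), 67% (10%, m = 2), 58% (20%, m = 2) and 39% (30%, m = 3). Type I error stayed between 4.2% and 5.5%. The direction is the same, and the size again depends on the assumptions.

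**Chance imbalance.** With 60 per arm and a share p of users, the between-arm difference in the number of users has SD √(2 × 60 × p(1 - p)). This is 3.3, 4.4 and 5.0 at p = 10%, 20% and 30%. A difference of five or more (4.5 with continuity correction) is 1.37, 1.03 and 0.90 SDs out, so it occurs in about 17%, 30% and 37% of trials. Without the field, no reader could tell whether this was such a trial.

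**The case against.** Several counter-arguments carry weight.

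- **A reader might infer that home opioid is counted as postoperative use.** The documents do not say so. The wording of 1.1 with the discharge list in 3.1 can mean discharge oxycodone only, while 8.1 and the survey in 7.1 point the other way. What stands is that the definition is missing.
- **A reader might infer that nothing collected could separate the two sources.** That goes too far. The survey asks which drugs were taken, so a home opioid other than oxycodone could be told apart. Patients whose home opioid is oxycodone are the ones who clearly cannot be separated.
- **A reader might see a fault in eligibility.** Investigator discretion in 4.2 could remove some users, although it sets no rule. A trial that includes prior users is legitimate. The gap lies in 3.1, 7.1 and 8.3.
- **The size is uncertain.** If users consume only 1.6 times as much, almost nothing is lost. It would also be wrong to promise that stratifying always restores 80%: model B shows that it does not. A yes/no flag cannot correct for daily dose either.
- **The consequence is limited.** The opioid endpoints are secondary whether the primary is complications (3.1) or pain scores (8.1). Section 8.2 refers only to complication rates, and an unadjusted rank test is valid.

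These points limit the weight of the concern. They do not remove it: an inexpensive and probably important baseline variable is missing, and two sections describe the opioid endpoint differently.

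**Conclusion.** The concern holds as a minor, inexpensive improvement. Three omissions are plain in the text: no stated criterion on opioid use, no preoperative opioid variable in 3.1 or 8.3, and no rule on which opioids enter the endpoints in 1.1 and 8.1. With the unstratified test, they put at risk the precision of the secondary opioid comparisons and leave any imbalance in prior users undetectable.

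The documents do not support a claim of systematic bias between arms, because randomization balances prior use in expectation. Nor do they support a claim that the primary outcome is affected.

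The loss runs from negligible to substantial. With 10-30% users, plain power falls from about 80% to as little as 60% under the proportional model, and from about 68% to 42% under the added-amount model. Stratifying gives about 80% and 75-61% respectively. These ranges rest wholly on the assumed N, effect, spread, prevalence and consumption of users. The direction is firmer: in these settings the stratified test never did materially worse than the plain one.

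**What to change.** 1. **Sections 3.1 and 8.3.** Add preoperative opioid use to the baseline data and the baseline table: yes/no, and daily dose if the medication list gives it. Parts of the plan are written in the past tense and 1.1 gives December 2021 as the end date, so the field may have to be filled from records.
2. **Section 8.3.** Compare oral morphine equivalents and opioid dose frequency with a van Elteren test stratified on preoperative use (yes/no), in place of the plain Mann-Whitney test.
3. **Section 7.1.** Record home and discharge opioids separately.
4. **Sections 1.1 and 8.1.** Use one stated definition of which opioids count, and report the other as a sensitivity analysis.

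Eligibility stays as it is. The cost is one field and a short syntax step in SPSS. Separating home from discharge opioid after the event may be impossible for patients who took the same drug from both sources, and the report should then say so.

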### 4.3 SCREEN FAILURES

N/A

### 4.4 STRATEGIES FOR RECRUITMENT AND RETENTION

Participants will be recruited to this study who present to the orthopaedic clinic with conditions that require arthroscopic rotator cuff repair.

## 5 STUDY INTERVENTION

### 5.1 STUDY INTERVENTION DESCRIPTION

Subjects will either receive ropivacaine interscalene catheter (control group) or single shot bupivacaine interscalene block with liposomal bupivacaine interscalene block as well (study group).

### 5.2 DOSING AND ADMINISTRATION

N/A

## 6 STUDY INTERVENTION DISCONTINUATION AND SUBJECT DISCONTINUATION/WITHDRAWAL

### 6.1 DISCONTINUATION OF STUDY INTERVENTION

If the subject experiences adverse effects of study intervention, the intervention will be withdrawn immediately.

### 6.2 SUBJECT DISCONTINUATION/WITHDRAWAL FROM THE STUDY

Subjects are free to withdraw from participation in the study at any time upon request.

An investigator may discontinue or withdraw a subject from the study for the following reasons:

- Significant study intervention non-compliance
- If any clinical adverse event (AE), laboratory abnormality, or other medical condition or situation occurs such that continued participation in the study would not be in the best interest of the subject

Subjects who sign the informed consent form and are randomized but do not receive the study intervention may be replaced. Subjects who sign the informed consent form, and are randomized and receive the study intervention, and subsequently withdraw, or are withdrawn or discontinued from the study, will not be replaced.

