## 1.2 SCHEDULE OF ACTIVITIES (SOA)

- *Screening/Consent Visit*
- *Randomization Visit*
- *Day of Surgery Visit*
- *Call 1: Evening after surgery (Day 0)*
- *Call 2: Day 1 morning*
- *Call 3: Day 1 evening*
- *Call 4: Day 2 morning*
- *Call 5: Day 2 evening*
- *Call 6: Day 3 morning*
- *Call 7: Day 3 evening*
- *Call 8: Day 4 morning*
- *Call 9: Day 4 evening*

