### 2.2 BACKGROUND

After orthopaedic surgery, patients experience exquisite levels of pain due to the large, invasive and disruptive procedures performed on the musculoskeletal system. Perioperative and post-operative pain management has traditionally involved regional anesthesia, utilizing sodium-channel blockers such as bupivacaine or ropivacaine. However, their short-acting nature requires continuous infusion via an implanted catheter that remains in place for 48-72 hours. This catheter is undesirable because it can become dislodged, requires the patient to manage it, as well as return days after surgery for removal.

A modified form of bupivacaine that is bound to lipid (liposomal bupivacaine) has been shown to have a much longer duration of action than the traditional sodium channel blockers. It is long enough that it could cover the same duration of pain as an implanted catheter and has generated interest in its potential use to control postoperative pain. Among patients undergoing total shoulder replacement, liposomal bupivacaine has shown to be non-inferior to standard catheter treatment, but there is a paucity of information on its use in rotator cuff repair. This study is meant to investigate the use of liposomal bupivacaine after arthroscopic shoulder surgery as compared to standard, catheter-infused ropivacaine.

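### Section 6.2 allows replacement and study withdrawal after randomisation while 8.3 defines no as-randomised analysis set, so the complication comparison could be biased by an unknown amount in either direction

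*Combined protocol and SAP*

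**What the plan says.** Section 6.2 contains three relevant provisions.

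- Replacement: "Subjects who sign the informed consent form and are randomized but do not receive the study intervention may be replaced". No arm is named, there is no cap, and nothing says how the replacement is allocated. Treated patients who "subsequently withdraw, or are withdrawn or discontinued from the study, will not be replaced".
- Withdrawal from the study by the investigator for "Significant study intervention non-compliance". The threshold for significant is not defined.
- Withdrawal from the study when an adverse event or other condition "occurs such that continued participation in the study would not be in the best interest of the subject".

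Stopping the intervention is a separate matter, in 6.1: "If the subject experiences adverse effects of study intervention, the intervention will be withdrawn immediately".

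Section 1.2 lists a "Randomization Visit" ahead of the day of surgery, so a patient can be randomised and never treated. The synopsis (1.1) describes a two-day infusion with a catheter that the patient removes, against a single injection. Section 2.2 says of the catheter: "This catheter is undesirable because it can become dislodged, requires the patient to manage it". Section 2.3.2 names knotting and falling out as catheter complications that the new block may avoid.

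Section 3.1 makes the overall complication rate the primary outcome. Section 8.1 names pain scores instead; the two must be reconciled, but this point applies to either. Section 8.3 gives Mann-Whitney and chi-squared tests. It defines no analysis set and no handling of untreated, replaced or withdrawn patients.

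**The concern.** Randomisation protects the comparison only if patients are counted in the arm they were assigned to. Here the protocol gives grounds for ending a patient's participation after allocation, and the analysis section does not say that the patient is still counted.

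The 6.2 rules are worded for both arms, but their triggers are not equally available. A two-day infusion run at home can be stopped early, mishandled or dislodged. Once a single injection has been given, there is little left to comply with or to withdraw. The adverse-event ground is also close to what the 3.1 outcome counts. Loss that differs by arm and is related to complications distorts the difference in complication rates. Pain is exposed to the same problem, because it is collected through calls up to Day 4 and study withdrawal may end those calls.

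**Working it through.** The plan offers no figure to reproduce. Section 8.2 gives power 0.8 and alpha 0.05, but no sample size, complication rates or dropout allowance. What follows is illustration, and every rate and loss is assumed.

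**Observed rate after loss.** Let p be the true catheter-arm risk, f the share of that arm lost and q the risk among those lost. Then observed rate = (p − f·q)/(1 − f). With p = 0.50:

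| f | q = 0.9 | q = 0.5 | q = 0.1 |
|---|---|---|---|
| 5% | (0.50 − 0.045)/0.95 = 47.9% | 50% | (0.50 − 0.005)/0.95 = 52.1% |
| 10% | (0.50 − 0.090)/0.90 = 45.6% | 50% | (0.50 − 0.010)/0.90 = 54.4% |
| 15% | (0.50 − 0.135)/0.85 = 42.9% | 50% | (0.50 − 0.015)/0.85 = 57.1% |

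The sign follows q. If those lost are complication-prone, the catheter looks better than it is, which works against the liposomal bupivacaine arm. If they are at low risk, the reverse holds. At average risk there is no bias.

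**Type I error.** Both arms have a true risk of 50%, 100 are randomised per arm, and only the catheter arm loses patients. They are not replaced, as 6.2 requires for treated patients, so 95, 90 or 85 remain. Exact binomial enumeration of the two-sided pooled test (equivalent to chi-squared without continuity correction) at nominal 5% gives:

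| Loss | q = 0.9 (or 0.1) | q = 0.7 |
|---|---|---|
| none | 5.6% | 5.6% |
| 5% | 5.7% | 5.0% |
| 10% | 9.5% | 6.2% |
| 15% | 16.1% | 7.8% |

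With 60 per arm and q = 0.9, the figures for 5%, 10% and 15% loss are 5.3%, 7.6% and 11.6%.

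**Power.** Assume true risks of 40% (catheter) and 20%, with 82 per arm for 80% power. Take the extreme case that everyone lost from the catheter arm had an uncounted complication (q = 1). The observed catheter rate is (0.40 − f)/(1 − f) = 36.8%, 33.3% or 29.4%, and power falls to about 66%, 47% or 27%.

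Small losses, or losses only moderately related to complications, therefore do little harm. Losses of 10% or more that are strongly related to complications do matter.

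**The case against.** A reader might infer that these losses fall mainly or only on the catheter arm and do bias the result. The documents do not support that.

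- No section gives losses by arm. A cancelled operation after the randomization visit can leave a patient in either arm untreated. More loss in the catheter arm is a reasonable inference, not a stated fact.
- Replacement is optional and does not itself delete the original patient. The gap is that nothing says the patient is kept. Failed threading is also a doubtful route to replacement: by the synopsis the ropivacaine bolus goes in through the needle first, so that patient has arguably been treated.
- Adverse-event withdrawal is limited to the patient's best interest, and the triggering event should already be recorded. Section 7.2.4 continues recording for 7 days (30 for serious events) after participation ends, which would span Day 0 to Day 4 for a patient withdrawn after surgery.
- Failed placement, dislodgement and early removal are not among the complications listed in 3.1 and 8.3. At most they enter through self-report.
- The illustrated inflation needs an extreme risk, 90% or 10%, among those lost.

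All of this stands, and it limits the claim to possible bias. It does not remove the gap. The plan does not say that the 7.2.4 records feed the endpoint, and it nowhere commits to analysing patients as randomised.

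**Conclusion.** The point holds as a risk. Following the plan as written can lose patients for reasons tied to the arm and to the complication outcome, and nothing in 8.3 brings them back into the analysis. This is more than missing detail, because 6.2 expressly permits withdrawal from the whole study for intervention non-compliance.

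Size and direction are unknown. On the assumed inputs, the effect on type I error runs from negligible at 5% loss to about 16.1% at 15% loss with 90% risk among those lost. It is nil if those lost are at average risk. The likelier mechanism, loss of complication-prone catheter patients, would understate catheter complications. That direction rests on how the two techniques differ, not on any data in the documents. The change should be made because it is cheap, not because bias has been shown.

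**What to change.** 1. In 8.3, state that the primary analysis includes all randomised patients in the arm assigned, including any who were untreated, replaced or withdrawn, and say how those without call data are counted.
2. In 6.2, remove intervention non-compliance as a ground for withdrawal from the study. State that stopping the intervention does not stop the Day 0 to Day 4 calls or the 12-week scores unless consent is withdrawn. The rule in 6.1 and the best-interest ground need no change for this purpose.
3. Report replacements and withdrawals by arm, with reasons.
4. Report catheter failure (failed placement, dislodgement, early removal) descriptively or in a sensitivity analysis. Do not add it to the primary complication rate, since that would change the endpoint.
5. Give a treated-set analysis as supportive.

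The cost is a few sentences, a few extra calls, and slight dilution of the effect by untreated patients. Sections 3.1 and 8.3 are written partly in the past tense. If follow-up is already over, the extra calls may no longer be possible, but items 1, 3 and 5 can still be applied, as can item 4 as far as catheter failures were recorded.
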